6.2 Antitumor Effect

For the purposes of this study, patients should be re-evaluated for response at 6 weeks, 12 weeks and then every 2 cycles thereafter. In addition to a baseline scan, confirmatory scans should also be obtained a minimum of 4 weeks following initial documentation of objective response. The investigator may opt to have the follow up scan performed according to the schedule (without an extra scan) as this follows the intent of the RECIST guidelines.

Response and progression will be evaluated in this study using the Response Evaluation Criteria in Solid Tumors (RECIST) Committee, version 1.1.64 Changes in only the largest diameter (unidimensional measurement) of the tumor lesions are used in the RECIST criteria, as defined below. In contrast, measurable disease in lymph nodes is determined based on the lymph node short axis.

6.3 Valuable for objective response:

All patients enrolled in the study should be assessed for response to treatment, even if there are major protocol treatment deviations or patients exhibit objective disease progression prior to the end of cycle 1.

All conclusions should be based on all enrolled patients. Subanalyses may then be performed on the basis of a subset of patients, excluding those for whom major protocol deviations have been identified (e.g., early death due to other reasons, early discontinuation of treatment, treating an ineligible patient, major protocol violations, etc.). However, these subanalyses may not serve as the basis for drawing conclusions concerning treatment efficacy, and the reasons for excluding patients from the analysis should be clearly reported. The 95% confidence intervals for response rate should also be provided.

All patients who were enrolled on the trial should be included in the main analysis of the response rate. Thus, an incorrect treatment schedule or drug administration does not result in exclusion. However, if a patient is removed from treatment prior to their 12 week assessment for reasons other than disease progression or death, they will be considered non-evaluable for response if approved by the DMC.

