10.0 STATISTICAL CONSIDERATIONS

10.1 Study Design/Study Endpoints

This is a single arm two-stage Simon optimum Phase II study of pazopanib and topotecan with progression-free rate at 12 weeks as the primary outcome. The historic PD free rate at 12 weeks for single agent pazopanib is 55%. To detect a 20% improvement (an 11% absolute improvement) with the combination of pazopanib and topotecan in a single-arm two-stage optimum design and a one-tailed exact binomial p- value, a total of 92 evaluable STS patients is required to detect 55% vs 66% with 80%

power and an alpha level of 10%. If 32 out of the first 55 patients are alive and progression free at 12 weeks, the trial may enroll up to 108 patients in order to acquire a total of 92 evaluable patients. At that time, if 56 or more out of 92 are alive and progression-free at 12 weeks, then the trial will conclude that the true 12 week PFS rate is at least 66%. There is a 63% probability of terminating the study after the first stage when the true rate is 55%. See sections 6.0 and 7.0 for definitions of evaluable patients for response and adverse event information.

Osteosarcoma/Liposarcoma exploratory group:

Up to 36 patients with osteosarcoma and 20 patients with liposarcoma will be enrolled to obtain exploratory information for patients with these two histologies. Although the sample sizes in these two cohorts were selected for feasibility rather than to power a specific hypothesis, 56 subjects will provide estimates of PFR and OS with sufficient precision to support additional study of pazopanib in these patients.

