10.2 Sample Size and Accrual

A total of 92 evaluable STS patients is required to detect 55% vs 66% with 80% power and an alpha level of 10%. If 32 out of the first 55 patients are alive and progression free at 12 weeks, this trial may enroll up to 108 STS patients in order to accrue a total of 92 evaluable patients. If the trial has not yet achieved 32 responses, may be suspended to enrollment to allow the 55th patient to reach week 12 of treatment for evaluation.

In addition, up to 36 patients with osteosarcoma and 20 patients with liposarcoma will be enrolled to obtain exploratory information for patients with these two histologies. Data exists to help construct baseline event free survival outcomes that can be used as a comparison for future phase II trials for recurrent osteosarcoma ([J Clin Oncol](#). 2016 Sep 1;34(25):3031-8. doi: 10.1200/JCO.2015.65.5381. Epub 2016 Jul 11.)

Using a single arm, 2 stage Phase II trial design: For stage I- If 4 or more of 19 patients have disease control of greater than 4 months then Stage 2 should be opened. The endpoint is that if 11 or more patients/ 36 have disease control at 4 months, then the agent is considered sufficiently efficacious for additional study.

As the study has been using 12 week and 20 week endpoints, we can use 20 weeks instead of 16 weeks as a surrogate endpoint.

The DMC reviewed the interim analysis data on 1/11/2017, and has approved cohort 1 to reopen to 96 total patients(to obtain 92 evaluable patients). In addition, based on the percentage of non-evaluable patients during the interim analysis, it was determined that a total of 108 patients would most likely need to be enrolled in order to obtain 92 evaluable patients.

The remaining slots have been equally divided in 5 ways among the sites, with an expiration date of May 12, 2017. Status of accrual will be reassessed at that time, and the remaining slots will be divided accordingly.

The 16 additional osteosarcoma slots will only be available at Northwestern (NMH).

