10.3 Data Analyses Plans

PFR and OS will be estimated for each histologic group (STS, osteosarcoma, and liposarcoma) using Kaplan-Meier methods. Response rates will be summarized by the observed proportion of patients with response, along with a 95% confidence interval. Toxicities will be tabulated and summarized by the number of patients experiencing each toxicity. A formal hypothesis test for the median PFR of the STS patients is planned; no formal hypothesis test is planned for the other two histologic groups.

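### Section 6.3 bars efficacy conclusions from sets that drop early stoppers, yet the STS decision rule in 10.1 is run on such a set

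*Combined protocol and SAP*

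**What the plan says.** Section 6.3 states a general rule: "All conclusions should be based on all enrolled patients". It allows subset analyses that leave out patients with major deviations and lists early discontinuation of treatment among the examples, but adds that "these subanalyses may not serve as the basis for drawing conclusions concerning treatment efficacy". It also puts every enrolled patient in the main response-rate analysis.

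The last sentence of 6.3 then says that patients removed from treatment before the 12-week assessment for "reasons other than disease progression or death, they will be considered non-evaluable for response if approved by the DMC". The document gives no criteria for that approval; the data safety monitoring plan is external.

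Section 10.1 imports the definition: "See sections 6.0 and 7.0 for definitions of evaluable patients for response and adverse event information". The STS rule is to continue at 32 of the first 55 and to declare success "if 56 or more out of 92 are alive and progression-free at 12 weeks", where 92 is the evaluable number. Section 10.2 allows for exclusions: "based on the percentage of non-evaluable patients during the interim analysis, it was determined that a total of 108 patients" would most likely be needed to reach 92. The replacement rule in 4.8 covers only patients who never received a dose.

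On week-12 status after early stopping, the section 5.0 footnotes schedule scans at weeks 6, 12 and 20. Section 6.1.4.1 asks for progression to be documented after stopping, but only for symptomatic deterioration. Section 4.6 follows patients without progression every 6 months, possibly by phone.

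**The concern.** The general rule and the decision rule name different populations, and the document does not say which governs the efficacy conclusion. The population actually used for the decision is selected after treatment began, and selected by outcome. A patient who progresses at week 6 counts as a failure. A patient who stops at week 6 without progression can be removed from the denominator, whatever would have been seen at week 12.

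The stated alpha and power therefore describe all treated patients only if those excluded have the same 12-week progression-free rate as the rest. The plan does not say whether the historic 55% counted early stoppers as failures, so it is also unclear which denominator matches the benchmark. And because no rule assigns week-12 status after early stopping, an all-patient result cannot be reconstructed in an agreed way.

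Two other rules are separate and not at issue here: the osteosarcoma rule ("if 11 or more patients/ 36 have disease control at 4 months") and the test in 10.3 ("A formal hypothesis test for the median PFR of the STS patients is planned").

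**Working it through.** **Inputs from 10.1 and 10.2.** Null 55%, target 66%, one-sided alpha 10%, power 80%; stage 1 continues at ≥32/55; final n = 92, success at ≥56; up to 108 enrolled, earlier 96. The ceilings on exclusions are 108 − 92 = 16 (14.8%) and 96 − 92 = 4 (4.2%). Either may include undosed patients.

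**Assumptions not in the documents.** The true rate in all treated patients is 55%; q is the 12-week progression-free rate in excluded patients; the 55 in stage 1 are evaluable patients (10.1 does not say).

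**1. The plan's own figures.** Early termination = P(X ≤ 31 | 55, 0.55) = 63.1%, matching the stated 63%. The pass probability for cut-off c is the sum over x = 32 to 55 of P(X₁ = x | 55, p) × P(X₂ ≥ c − x | 37, p).
- c = 56 (as printed): alpha 13.6%, power 84.3%.
- c = 57: alpha 10.0%, power 80.3%.

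The one-patient difference in the cut-off is a separate matter, so both are carried through.

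**2. Exclusions with an assumed q.** With fraction d excluded, the evaluable rate is e = (0.55 − d·q)/(1 − d). Example: d = 16/108 and q = 0.40 give (0.55 − 0.0593)/0.8519 = 0.576.

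**3. Stopping independent of progression.** Assume constant hazards per 12 weeks. The progression hazard is λ = −ln 0.55 = 0.598 and the stopping hazard is μ. Then d = [μ/(λ+μ)]·[1 − exp(−(λ+μ))] and q = 0.55·[1 − exp(−μ)]/d. For d = 16/108, μ = 0.217, q = 0.72 and e = 0.520. Here q exceeds 55% because a patient must still be progression-free when stopping in order to be excluded.

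| Excluded | q | e | Pass at 56 | Pass at 57 |
|---|---|---|---|---|
| any | 55% (no bias) | 55.0% | 13.6% | 10.0% |
| 16/108 | 72% (independent stopping) | 52.0% | 4.8% | 3.2% |
| 16/108 | 65% | 53.3% | 7.7% | 5.3% |
| 16/108 | 40% | 57.6% | 27% | 22% |
| 16/108 | 25% | 60.2% | 46% | 39% |
| 4/96 | 73% (independent stopping) | 54.2% | 10.6% | 7.6% |
| 4/96 | 40% | 55.7% | 16.5% | 12.4% |

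**4. Power under independent stopping.** Put 0.66 in place of 0.55 in step 3 and keep 16/108 excluded: λ = 0.416, μ = 0.198, q = 0.80, e = 0.635. Power is 70% at cut-off 56 and 64% at 57, against 84% and 80% without bias.

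**5. Bounds on a just-passing result.** 56/92 = 60.9%. If 16 further dosed patients have unknown status, the rate in all dosed patients lies between 56/108 = 51.9% and 72/108 = 66.7%. That interval contains both the 55% null and the 66% target. With 4 unknown it is 56/96 = 58.3% to 60/96 = 62.5%.

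**The case against.** The strongest reply is that the last sentence of 6.3 opens with *However*, so it is a specific exception to a general rule, and that 10.1 adopts it by cross-reference. As a reading of intent this is reasonable. It does not remove the conflict: 6.3 never says that the evaluable set may support an efficacy conclusion, and that set is of the very kind it bars.

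Second, part of the remedy is already in the plan. Section 6.3 requires reasons for exclusion to be reported (stated for subanalyses), 10.3 already plans Kaplan-Meier estimation for STS, and 4.6 provides progression follow-up for patients without progression. The DMC's criteria may be in the external monitoring plan. The section 5.0 schedule grid was not in the text available, only its footnotes, so end-of-treatment imaging cannot be judged. All of this stands, and it makes the fix small.

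Third, the rule may already be conservative. This stands too. A reader might infer that dropping early stoppers must favour the combination; under independent stopping the rule is too strict and loses power. A reader might also infer that it is enough for stopping to be uninformative in the Kaplan-Meier sense. Step 3 of the working shows that it is not: independent stopping gives q of about 72%, not 55%.

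**Conclusion.** The point holds as an internal contradiction, and that part needs no assumption: 6.3 and 10.1 cannot both govern the STS efficacy conclusion as written. It should be fixed because the choice of set can change the primary conclusion.

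The numerical consequence is conditional. At the 16/108 ceiling the pass probability at cut-off 56 runs from 4.8% to 46% over q from 72% down to 25%. At 4/96 it runs from 10.6% to 16.5% over q from 73% down to 40%. These figures rest on assumed values of q, a true all-treated rate of 55% and, for the independent-stopping rows, constant hazards.

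The documents do not support saying that the type I error is inflated, nor that 16 dosed patients were excluded. The number 16 is an enrolment allowance, and the interim non-evaluable percentage is not given.

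**What to change.** All of the following should be dated before the final analysis, since accrual is closed and the interim has been reviewed.

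1. Name one analysis set for the STS decision rule, in the same words in 6.3 and 10.1. If the evaluable set stays, say that it is the exception to the all-enrolled sentences, and give or cite the DMC's criteria.
2. State how week-12 status is assigned after early stopping. A scan at or after week 12 without progression means progression-free at week 12. Clinical deterioration and death count as events, as in 6.5. Say how scans after new anticancer therapy are handled.
3. Report the 12-week rate in all dosed STS patients beside the evaluable result, with unknown status counted as not progression-free (lower bound) and as progression-free (upper bound). Give the 12-week estimate from the Kaplan-Meier analysis already planned. It assumes stopping independent of progression, so it does not replace the bounds. Extend the existing duty to report reasons to every DMC-approved exclusion.
4. State whether 55% and 66% refer to treated or evaluable patients. Add that alpha and power on the evaluable set apply to all treated patients only if excluded patients have the same 12-week rate as the rest. Avoid the word *uninformative* for this condition.

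A new hurdle for success is not needed. If the sponsor wished to require a lower bound of at least 55%, 16 unknown patients would mean 60/92 (60/108 = 55.6%), and power at a 66% evaluable rate would fall from 84% to 61%. Moving the decision to all dosed patients is likewise optional and would need a recomputed cut-off.

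Cost: wording in 6.3 and 10.1 to 10.3, one extra analysis and a listing of exclusions. The reported rate may look less favourable. No new patients are needed.

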6.4 Methods for Evaluation of Measurable Disease

All measurements should be taken and recorded in metric notation using a ruler or calipers. All baseline evaluations should be performed as closely as possible to the beginning of treatment and never more than 4 weeks before the beginning of the treatment.

The same method of assessment and the same technique should be used to characterize each identified and reported lesion at baseline and during follow-up. Imaging-based evaluation is preferred to evaluation by clinical examination when both methods have been used to assess the antitumor effect of a treatment.

Clinical lesions will only be considered measurable when they are superficial (e.g., skin nodules and palpable lymph nodes). In the case of skin lesions, documentation by color photography, including a ruler to estimate the size of the lesion, is recommended.

Chest x-ray

Lesions on chest x-ray are acceptable as measurable lesions when they are clearly defined and surrounded by aerated lung. However, CT is preferable.

Conventional CT and MRI

These techniques should be performed with cuts of 10 mm or less in slice thickness contiguously. Spiral CT should be performed using a 5 mm contiguous reconstruction algorithm. This applies to tumors of the chest, abdomen, and pelvis. Head and neck tumors and those of extremities usually require specific protocols.

Cytology, Histology

The cytological confirmation of the neoplastic origin of any effusion that appears or worsens during treatment when the measurable tumor has met criteria for response or stable disease is or stable disease (an effusion may be a side effect of the treatment) and progressive disease

6.5 Primary Endpoint

Time from enrollment to progression, with progression defined as changes in RECIST 1.1 defined imaging, progression in non-target lesions as defined by RECIST 1.1, unequivocal clinical deterioration, or death from any cause.

6.6 Secondary Endpoints

- The presence of response (ORR- CR+PR) per RECIST version 1.1 in cohort 1.
- The presence of clinical benefit (CR+ PR + SD) per RECIST version 1.1 in cohort 1.
- The time from the first dose of the study treatment until death from any cause, up to a maximum follow-up of two years.
- The endpoint is to determine OS for patients with STS treated with combination pazopanib and topotecan.
- The presence of all toxicities outlined in NCI CTCAE version 4.03 from time of first treatment.
- The endpoint for patients with osteosarcoma, time from treatment to progression, based upon changes in RECIST 1.1 defined imaging, progression in non-target lesions as defined by RECIST 1.1, unequivocal clinical deterioration, or death from any cause.
- The endpoint for patients with liposarcoma, time from treatment to progression based upon changes in RECIST 1.1 defined imaging, progression in non-target lesions as defined by RECIST 1.1, unequivocal clinical deterioration, or death from any cause.

6.7 Exploratory Endpoint

For cohort 1 and 3: Quantify Cell-free circulating tumor DNA (ctDNA) at each time point, and correlate these results with demographic, diagnostic, treatment, and outcomes data. For cohort 2: Verification of results of Sleijfer et al and to determine if there is an even earlier correlation that can be detected between levels of these cytokines and PFR as well as OS which may allow us to better predict treatment response early on in therapy

7.0 ADVERSE EVENTS

This study will be conducted in compliance with the Data Safety Monitoring Plan (DSMP) of the Robert H. Lurie Comprehensive Cancer Center of Northwestern University (<http://cancer.northwestern.edu/CRO/data/DataandSafetyMonitoringPlanMay2014.pdf>). The level of risk attributed to this study requires high-intensity monitoring as outlined in the DSMP.

7.1 Adverse Event Monitoring

Adverse event data collection and reporting, which are required as part of every clinical trial, are done to ensure the safety of subjects enrolled in the studies as well as those who will enroll in future studies using similar agents. Adverse events are reported in a routine manner at scheduled times during a trial (see Section 5 for timepoints). In addition, certain adverse events must be reported in an expedited manner to allow for optimal monitoring and patient safety and care.

All patients experiencing an adverse event, regardless of its relationship to study drug, will be followed until:

- the adverse event resolves or the symptoms or signs that constitute the adverse event return to baseline;
- any abnormal laboratory values have returned to baseline;
- there is a satisfactory explanation other than the study drug for the changes observed; or
- death.

7.2 Definitions & Descriptions

7.2.1 Adverse Event

An adverse event (AE) is any untoward medical occurrence in a patient receiving study treatment and which does not necessarily have a causal relationship with this treatment. An AE can therefore be any unfavorable and unintended sign (including an abnormal laboratory finding), symptom, or disease temporally associated with the use of an experimental intervention, whether or not related to the intervention.

Recording of AEs should be done in a concise manner using standard, acceptable medical terms. In general, AEs are not procedures or measurements, but should reflect the reason for the procedure or the diagnosis based on the abnormal measurement. Preexisting conditions that worsen in severity or frequency during the study should also be recorded (a preexisting condition that does not worsen is not an AE). Further, a procedure or surgery is not an AE; rather, the event leading to the procedure or surgery is considered an AE.

If a specific medical diagnosis has been made, that diagnosis or syndrome should be recorded as the AE whenever possible. However, a complete description of the signs, symptoms and investigations which led to the diagnosis should be provided. For example, if clinically significant elevations of liver function tests are known to be secondary to hepatitis, "hepatitis" and not "elevated liver function tests" should be recorded. If the cause is not known, the abnormal test or finding should be recorded as an AE, using appropriate medical terminology (e/g/ thrombocytopenia, peripheral edema, QT prolongation).

7.2.2 Severity of AEs

All non-hematologic adverse events will be graded according to the NCI Common Terminology Criteria for Adverse Events (CTCAE) version 4.03. The CTCAE v4.03 is available at <http://ctep.cancer.gov/reporting/ctc.html>

If no CTCAE grading is available, the severity of an AE is graded as follows:

- Mild (grade 1): the event causes discomfort without disruption of normal daily activities.
- Moderate (grade 2): the event causes discomfort that affects normal daily activities.
- Severe (grade 3): the event makes the patient unable to perform normal daily activities or significantly affects his/her clinical status.
- Life-threatening (grade 4): the patient was at risk of death at the time of the event.
- Fatal (grade 5): the event caused death.

7.2.3 Serious Adverse Events (SAEs)

All SAEs, regardless of attribution, occurring from time of signed informed consent, through 30 days after the last administration of study drug, must be reported upon discovery or occurrence.

An SAE is defined in regulatory terminology as any untoward medical occurrence that:

- **Results in death.**
If death results from (progression of) the disease, the disease should be reported as event (SAE) itself.
- **Is life-threatening.**
The patient was at risk of death at the time of the event; it does not refer to an event that hypothetically might have caused death if it were more severe.
- **Requires in-patient hospitalization or prolongation of existing hospitalization for \geq 24 hours.**
- **Results in persistent or significant disability or incapacity.**
- **Is a congenital anomaly/birth defect.**
- **Is an important medical event.**

Any event that does not meet the above criteria, but that in the judgment of the investigator jeopardizes the patient, may be considered for reporting as a serious adverse event. The event may require medical or surgical intervention to prevent one of the outcomes listed in the definition of "Serious Adverse Event".

For example: allergic bronchospasm requiring intensive treatment in an emergency room or at home; convulsions that may not result in hospitalization; development of drug abuse or drug dependency.

